14.2 Secondary Endpoint

14.2.1 Long-term disability status

The secondary efficacy endpoint of this study will be evaluated descriptively by percentage and 95% CI of patients with EDSS of 6.0 or higher since last dose of IMP until Visit 1. The results of the confidence scale of EDSS values will be presented descriptively for worst EDSS score (available only for Retro EDSS). The worst EDSS value will be summarized by categories for each cohort.

EDSS will be assessed clinically (on site) and by phone.

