8.1.1 Clinical Endpoints

8.1.1.1 Expanded Disability Status Scale (EDSS)

The EDSS is a neurological assessment that will be used to assess the long-term disability progression following treatment with IMP in the parent studies (Appendix 5 Expanded Disability Status Scale (EDSS)). EDSS is a scale from 0-10 that evaluates a person with MS's disability/neurologic function level with 6 being the critical point at which a patient requires ambulatory assistance. The primary endpoint of proportion of study participants using a wheelchair (defined as unable to walk beyond approximately 5 meters even with aid,

essentially restricted to wheelchair; wheels self in standard wheelchair and transfers alone; up and about in wheelchair some 12 hours a day) the majority of the time in the 3 months prior to Study Visit 1 or participants are bedridden any time prior to Study Visit 1 determined via an EDSS score of 7.0 or higher (if available), or alternative clinical description data in medical records. The secondary endpoint will be determined as the proportion of study participants with EDSS of 6.0 or higher by EDSS documentation or alternative clinical description in medical records after last IMP from parent study.

Sustained disease progression is important because transient increases in the EDSS may also be due to relapses, which reflect disease activity rather than disease progression (Healy, 2013); an EDSS measurement taken at a single point in time may be subject to measurement error (Goodkin, 1992). As such, confirmation of sustained EDSS score is needed to mitigate against measurement error and EDSS fluctuation (Kalincik, 2015).

Furthermore, while EDSS scores at any timepoint, regardless of their relationship to relapses, may serve as evidence of EDSS progression, it is generally recommended that only EDSS scores that are recorded more than 30 days from the onset of a preceding relapse be used in order to confirm progression events (Kalincik, 2015). As such, Investigators in this study will be instructed to exclude any EDSS score recorded within 30 days of a previous relapse.

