The in-person EDSS will be completed by the evaluating physician for those study participants who can come to the clinic for Study Visit 1. Alternatively, a telephone EDSS score can be determined by telephone interview in which trained clinical site staff member to administer the EDSS telephone questionnaire (Lechner-Scott, 2003). The telephone EDSS will be collected only from patients not attending clinic visits, and will be collected within 14 days of obtaining informed consent. Only one mode of the collection (in-person during a clinic visit, or by telephone) is required per patient. Retrospective EDSS scores will be ascertained from medical records for the time period between end of parent study to Study Visit 1 (when available).

Reasons for inability to come to the clinic for Study Visit 1 may include travel/migration, or limited mobility (bedridden), or clinical site restrictions due to COVID-19. In addition, patients may not want to come to the clinic for Study Visit 1 due to a lack of interest..

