8.1.2.2 Frequency of Stable Patient Monitoring Questions

Each evaluating physician at the clinical sites will be asked to complete questions assessing how frequently the study patients with MS are monitored and evaluated at their site in regular clinical practice. These questions ask about frequency of follow-up visits and follow-up MRI assessments if the study patients with MS are considered stable.

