Table 15.2.2.2.8	Proportion of patients with EDSS of 6.0 or higher since last dose of IMP– Cohort B- FAS analysis set- Subset Long-term Responder (Sensitivity Def C)		
Table 15.2.2.3.1	Proportion of patients with EDSS of 6.0 or higher since last dose of IMP –Cohort C- FAS analysis set		
Table 15.2.2.3.2	Proportion of patients with EDSS of 6.0 or higher since last dose of IMP –Cohort C- FAS analysis set- Subset Long-term Responder		

Table 15.2.2.3.3	Proportion of patients with EDSS of 6.0 or higher since last dose of IMP –Cohort C- FAS analysis set- Subset Types of Subsequent DMDs		
Table 15.2.2.3.4	Proportion of patients with EDSS of 6.0 or higher since last dose of IMP– Cohort C- FAS analysis set- Subset Long-term Responder (Sensitivity Def B)		
Table 15.2.2.3.5	Proportion of patients with EDSS of 6.0 or higher since last dose of IMP– Cohort C- FAS analysis set- Subset Long-term Responder (Sensitivity Def C)		
Table 15.2.2.4.1	Proportion of patients with EDSS of 6.0 or higher since last dose of IMP –Cohort D- FAS analysis set		
Table 15.2.2.4.2	Proportion of patients with EDSS of 6.0 or higher since last dose of IMP –Cohort D- FAS analysis set- Subset Long-term Responders		
Table 15.2.2.4.3	Proportion of patients with EDSS of 6.0 or higher since last dose of IMP –Cohort D- FAS analysis set- Subset Types of Subsequent DMDs		
Table 15.2.2.4.4	Proportion of patients with EDSS of 6.0 or higher since last dose of IMP– Cohort D- FAS analysis set- Subset Long-term Responder (Sensitivity Def B)		
Table 15.2.2.4.5	Proportion of patients with EDSS of 6.0 or higher since last dose of IMP– Cohort D- FAS analysis set- Subset Long-term Responder (Sensitivity Def C)		
Table 15.2.2.5.1	Worse EDSS since last dose of IMP – Cohort A – FAS analysis set	Y	U
15.2.3: Secondary Endpoint 2			
Table 15.2.3.1.1	Clinical characteristics at Study Visit 1 of long-term responders vs non-responders –Cohort A -FAS analysis set	Y	U
Table 15.2.3.1.2	Clinical characteristics at Study Visit 1 of long-term responders vs non-responders –Cohort A -FAS analysis set (Sensitivity Def B)		
Table 15.2.3.1.3	Clinical characteristics at Study Visit 1 of long-term responders vs non-responders –Cohort A -FAS analysis set (Sensitivity Def C)		
Table 15.2.3.2.1	Clinical characteristics at Study Visit 1 of long-term responders vs non-responders – Cohort B -FAS analysis set		

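### The EDSS 6.0 secondary endpoint counts any one unconfirmed score out of an uneven number of chart scores, so rater noise near the threshold can create events; a confirmed sensitivity analysis and a table of score counts are missing.

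*SAP*

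**What the plan says.** Protocol 8.1.1.1 defines the secondary endpoint as the "proportion of study participants with EDSS of 6.0 or higher by EDSS documentation or alternative clinical description in medical records after last IMP" in the parent study. SAP 14.2.1 turns this into a percentage with 95% CI of "patients with EDSS of 6.0 or higher since last dose of IMP until Visit 1". It adds that "The worst EDSS value will be summarized by categories for each cohort", and the output list in SAP Appendix 17.1 has a matching table (15.2.2.5.1, "Worse EDSS since last dose of IMP"). Neither document gives a confirmation rule for this endpoint.

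Protocol 8.1.1.1 also warns that "an EDSS measurement taken at a single point in time may be subject to measurement error" and that "confirmation of sustained EDSS score is needed to mitigate against measurement error and EDSS fluctuation".

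The number of scores per participant is not fixed. For the years between the parent trial and SV1 the protocol takes whatever scores the chart contains. Protocol 8.1.2.2 asks physicians "how frequently the study patients with MS are monitored and evaluated at their site in regular clinical practice", so visit frequency follows local habit.

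Two safeguards exist. Investigators are told to leave out scores recorded within 30 days of a relapse (Protocol 8.1.1.1). A non-validated four-point confidence rating accompanies EDSS scores (Protocol 8.1.1.2); SAP 14.2.1 presents it descriptively for the worst score, and Protocol 9.4 says it may help interpretation. A requirement for sustained worsening appears only in the SPMS definitions (Protocol 8.1.1.9 and 8.1.1.10).

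**The concern.** An event that needs only one score at or above 6.0 is the same as a maximum at or above 6.0. The maximum of noisy readings rises with the number of readings, even when the patient does not change. The relapse exclusion removes fluctuation tied to relapses, not rater error. The confidence rating does not stop a doubtful score from counting.

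The proportion therefore mixes disability with intensity of documentation. SAP 14 presents results by parent-study exposure, and the output list repeats this endpoint by responder status, type of subsequent DMD and other subgroups. If score counts differ between these groups, part of any difference may reflect the counts. SAP 9.5 rests interpretation on point estimates and 95% CIs, and a CI does not show this kind of bias.

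**Working it through.** **No planned figure exists for this endpoint.** The only precision figures (Protocol 9.2) concern the wheelchair endpoint. I reproduce one row as a yardstick. For n = 587 and p = 15%, the half-width is 1.96 × √(0.15 × 0.85 / 587) × √((1958 − 587) / 1957) = 2.89 × 0.837 = 2.42 points, as printed. The second root is a finite population correction.

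**Inputs.** From the documents: the threshold of 6.0, the any-time rule, the half-point scale and the unfixed number of scores. Assumed, because the documents do not give them:
- independent normal rater error with SD s = 0.35 to 0.50;
- k = 2, 10 or 20 scores;
- 15% of participants at a stable true EDSS just below the threshold, split 5%, 4%, 3% and 3% at 4.0, 4.5, 5.0 and 5.5.

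**Formulas.** With rounding to half points, a score reads 6.0 or higher when true value plus error is at least 5.75.
- One score: q = 1 − Φ((5.75 − t) / s), where t is the true EDSS.
- Any of k scores: 1 − (1 − q)^k.
- Confirmed rule (two consecutive scores at or above 6.0, or the last score at or above 6.0): let a be the probability of no confirmed event with the latest score below 6.0, and b the same with the latest score at or above 6.0. Start at a = 1, b = 0. At each score the new a is (a + b)(1 − q) and the new b is a × q. After k scores the event probability is 1 − a. If SV1 gives the last score, confirmation by SV1 is already covered.

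**One participant at true 5.0.** At s = 0.35, q = 1 − Φ(2.14) = 0.016. At s = 0.50, q = 1 − Φ(1.50) = 0.067.

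| Scores | Any score ≥ 6.0 | Confirmed rule |
|---|---|---|
| 2 | 3.2-12.9% | 1.6-6.7% |
| 10 | 14.9-49.9% | 1.8-9.8% |
| 20 | 27.7-74.9% | 2.1-13.5% |

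**Assumed cohort.** The excess is the sum over the four EDSS levels of share × event probability. For example, any-score with 10 scores at s = 0.35 gives 0.04 × 0.2% + 0.03 × 14.9% + 0.03 × 93.4% = 3.3 points (the 4.0 term is negligible).

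| Scores | Any score, added points | Confirmed rule, added points |
|---|---|---|
| 2 | 1.4-2.0 | 0.8-1.2 |
| 10 | 3.3-4.7 | 1.5-2.3 |
| 20 | 3.8-5.7 | 2.1-3.0 |

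Most of the excess comes from participants at 5.5 (2.8 of 3.3 points in the example). At s = 0.50, a participant at 4.0 has only a 0.5% chance of an event even with 20 scores.

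**Dependence on score count.** From 2 to 20 scores the any-score excess grows by 2.5-3.7 points and the confirmed excess by 1.4-1.8. If half the error variance is a fixed offset per patient, the any-score growth is 1.6-2.3 points. Correlation therefore shrinks the growth without reversing it.

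**Cost in sensitivity.** At true 6.0 with 2 scores, detection falls from 90.5-94.4% (any score) to 69.1-76.2% (confirmed). With 10 scores the confirmed rule still detects over 99%.

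**The case against.** Several points on the other side stand, wholly or in part.

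- **Not a flat contradiction.** A reader might infer that the SAP breaks a protocol requirement. The protocol's sentence is about sustained progression, whereas the endpoint is a milestone proportion, and the operational step drawn from that discussion is the 30-day relapse exclusion. What remains is an unfilled gap in the section that defines this endpoint.
- **The error model is unsupported at this threshold.** Appendix 5 ties scores of 5.0 and above to walking ability: 5.0 is 200-299 m unaided, while 6.0 is under 100 m unaided or walking with unilateral assistance. The cited rater-agreement study covers grades 1.0 to 3.5, by its title. Errors near 6.0 may be smaller than assumed.
- **High score counts are unsupported.** SAP 8.2.2 expects retrospective EDSS to be missing or unreported for some participants. With 2 scores the excess is only 1.4-2.0 points.
- **Not all events rest on a chart score.** The protocol also admits clinical descriptions, and the window takes in the SV1 score and parent-study scores after the last dose.
- **Bias between exposure groups is unproven.** A reader might infer that the exposed versus never-exposed comparison is distorted. Nothing in the documents shows that score counts differ by exposure. Protocol 9.3 and SAP 8.2.2 already disclaim treatment-effect comparisons for the treatment-course and subsequent-DMD subgroups.

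The study's exploratory label does not dispose of the point, because the published estimate itself would carry the noise.

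**Conclusion.** The point holds as a gap with an inexpensive remedy. The any-time rule makes the EDSS 6.0 proportion depend partly on how many scores were recorded, for participants at a true EDSS of about 4.5 to 5.5, and neither existing safeguard deals with rater error. Under the stated assumptions the excess is 1.4 to 5.7 points across 2 to 20 scores. The yardstick of 2.42 points belongs to another endpoint and gives scale only. The direction follows from taking a maximum; the size rests on the assumed SD, score counts and EDSS mix.

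Two stronger readings go too far. One is that a stable patient with many scores will probably be miscounted: at true 5.0 with 20 scores the chance runs from 27.7% to 74.9%, so this depends on the SD. The other is that a confirmed definition should replace the endpoint: it leaves part of the dependence on score count and misses true events where scores are few. No type I error or power claim is affected, since no hypothesis is tested.

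**What to change.** In SAP 14.2.1:

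1. Keep the any-score proportion as planned.
2. Add a pre-specified sensitivity analysis: the proportion with EDSS 6.0 or higher confirmed by the next available score (retrospective, in-person or telephone) or by the SV1 score. A last-ever score of 6.0 or higher counts as an event, because no later score can refute it.
3. State how participants with a single score are handled, and how events that rest on a clinical description are treated.
4. Tabulate the number of EDSS scores per participant by exposure group and for each subgroup in which this endpoint is shown.

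The cost is SAP wording, one extra derivation and a count table, all from data already collected. The confirmed version loses sensitivity where scores are few, so the two proportions should be reported side by side and read with the counts.

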14.2.2 Clinical characteristics

The clinical characteristics of study participants will be evaluated descriptively by the subgroups long-term responders and non-responders for Cohort A as per section 9.5. Clinical and demographic characteristics include gender, age, race, ethnicity, region, EDSS Score, number of relapses during last year before enrollment of parent study, prior use of DMDs, HDA Status, education, employment status, time since last IMP (years), type of first DMD after last dose of IMP, disease duration, and disease classification.

14.2.3 MRI characteristics

The MRI characteristics of study participants in the MRI sub-study analysis will be evaluated descriptively at Study Visit 2 by the subgroups of long-term responders and non-responders for all Cohorts as per section 9.5.

The MRI characteristics of study participants in the MRI sub-study analysis include the following MRI variables:

- Number of total T2-W Lesions at Study Visit 2
- Number of total T1-W Lesions at Study Visit 2

- Volume of total T2-W Lesions (cm³) at Study Visit 2
- Volume of total T1-W Lesions (cm³) at Study Visit 2
- Brain Volume (cm³) at Study Visit 2

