
To evaluate differences in clinical characteristics between long-term responders and study participants requiring alternate therapies following treatment with IMP for the CLARITY/CLARITY-EXT and ORACLE MS populations.
	
Clinical characteristics^a at Study Visit 1 of long-term responders (defined as study participants who did not demonstrate any evidence of disease reactivation based on Investigator assessment of clinical and imaging outcomes until Year 4 or later following their last dose^b of IMP and who did not receive disease modifying treatment until Year 4 or later following their last dose^b of IMP) compared to those of other study participants who started on alternate therapy less than 4 years following their last dose^b of IMP for the CLARITY/CLARITY-EXT and ORACLE MS populations.

To evaluate differences in magnetic resonance imaging (MRI) characteristics between long-term responders and study participants requiring alternate therapies following treatment with IMP for the CLARITY/CLARITY-EXT and ORACLE MS populations.
	
MRI characteristics^c at Study Visit 2 of long-term responders (defined as study participants who did not demonstrate any evidence of disease reactivation based on Investigator assessment of clinical and imaging outcomes until Year 4 or later following their last dose^b of IMP and who did not receive disease modifying treatment until Year 4 or later following their last dose^b of IMP) compared to those of other study participants who started on alternate therapy less than 4 years following their last dose^b of IMP for the CLARITY/CLARITY-EXT and ORACLE MS populations.

Tertiary	

To assess the real-world treatment patterns in study participants previously treated with IMP as part of the Phase III ORACLE MS and CLARITY/CLARITY-EXT clinical trials.
	
Time, type, and reason for first sequential treatment after first course^b of IMP, type of second sequential treatment, as well as the frequency of routine clinical monitoring and disease activity status as well as clinical and demographic characteristics^a available for the CLARITY/CLARITY-EXT and ORACLE MS populations.

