ARR=Annualized Relapse Rate, BVMT-R=Brief Visuospatial Memory Test Revised, CDMS=Clinically Definite Multiple Sclerosis, EDSS=Expanded Disability Status Scale, EQ-5D=EuroQoL-5 Dimension, HDA=High-disease activity, IMP=Investigational Medicinal Product, MRI=Magnetic Resonance Imaging, MS=Multiple Sclerosis, PPMS=Primary Progressive MS, RRMS=Relapsing-Remitting Multiple Sclerosis, SDMT=Symbol Digit Modalities Test, SPMS=Secondary Progressive Multiple Sclerosis.

^a Specific clinical and demographic characteristics may include gender, age, race, ethnicity, education, disease duration, years previous disease modifying treatment (before start of CLARITY/CLARITY-EXT/ORACLE MS) and disease classification (RRMS or SPMS).

^b One dose is equivalent to one tablet. One course of IMP is defined as 1 year of treatment with IMP (2 treatment cycles [weeks]). A treatment cycle is defined as daily administration of IMP given consecutively over 4-5 days during a 28-day period. One treatment week is equivalent to 1 treatment cycle.

^c Total volume of T2 lesions; Total number of T2 lesions; Number of hypointense lesions on T1-spin echo MRI; Volume of hypointense lesions on T1-spin echo MRI; Brain volume or surrogate; Ventricular volume.

^d Mobility endpoints may be determined via EDSS scores (if available) or corresponding clinical descriptions in medical records.

^e 1. Patients with ≥ 2 relapses during the year prior to parent study entry, regardless of prior disease modifying drugs (DMD) use; 2. Patients with ≥ 1 relapse in the previous year and ≥ 1 T1 Gd+ lesions or ≥ 9 T2 lesions, while on therapy with other DMDs.

Overall Design: This Phase IV, low-interventional, multicenter, ambispective study will include study participants treated with Cladribine Tablets or placebo in the previously conducted parent studies. Long-term retrospective data will be collected through evaluation of medical charts/records (e.g., sociodemographic and clinical characteristics, medical and disease history, Secondary Progressive Multiple Sclerosis [SPMS] conversion, Expanded Disability Status Scale [EDSS], details of subsequent Disease Modifying Drugs (DMDs), including physician questions on treatment decisions, date of first use of an ambulatory device or wheelchair and relapse history from end of parent study to Study Visit 1 as well as, for ORACLE MS patients only, Clinically Definite MS conversion [CDMS] and Primary Progressive MS [PPMS] diagnosis).

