6.5 Final Analysis

All analyses described in this IAP will be performed after the final database lock (see Section 14

for further details on analyses) and summarized in final study report. Results of the final analysis will be summarized in a formal study report.

7 Changes to the Planned Analyses in the Clinical Study Protocol

There are no changes to the analyses planned per protocol.

8 Analysis Populations and Subgroups

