14.3.4 Durability of outcomes on brain imaging

Changes in MRI assessment from the last clinical visit in the parent studies (called “Screening”) to Study Visit 2 will be analyzed descriptively for the MRISS analysis population for the following MRI parameters.

- Changes in number of total T2-W Lesions from Screening to Study Visit 2 (only for ORACLE MS)
- Changes in number of total T1-W Lesions from Screening to Study Visit 2
- Percentage changes in volume of total T2-W Lesions from Screening to Study Visit 2 (only for

ORACLE MS)

- Percentage changes in volume of total T1-W Lesions from Screening to Study Visit 2
- Percentage in Brain Volume changes from Screening to Study Visit 2
- Percentage of ventricular Atrophy: Longitudinal from Screening to Study Visit 2

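### SAP 14.2.3 leaves ventricular volume out of the MRI secondary endpoint without declaring it; separately, its Study Visit 2 comparison shows no pre-treatment MRI value by responder status

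*SAP*

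**What the plan says.** The protocol defines the endpoint as MRI characteristics "at Study Visit 2 of long-term responders (defined as study participants who did not demonstrate any evidence of disease reactivation", with further conditions, compared with participants who started other therapy within 4 years of the last dose. Footnote c in the Protocol synopsis, repeated in SAP section 5, names six measures: T2 volume, T2 number, T1 hypointense number, T1 hypointense volume, and then "Brain volume or surrogate; Ventricular volume". Footnote c in Protocol section 3 lacks T1 volume but keeps ventricular volume.

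SAP 14.2.3 states that the characteristics "will be evaluated descriptively at Study Visit 2 by the subgroups of long-term responders and non-responders". It lists T2 and T1 lesion numbers, T2 and T1 lesion volumes, and "Brain Volume (cm³) at Study Visit 2". SAP section 7 states: "There are no changes to the analyses planned per protocol".

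Change over time is a separate tertiary analysis in SAP 14.3.4, where changes from the last parent-study clinical visit "to Study Visit 2 will be analyzed descriptively for the MRISS analysis population". It includes "Percentage in Brain Volume changes from Screening to Study Visit 2" and a longitudinal ventricular atrophy measure. Change in T2 number and T2 volume is planned for ORACLE MS only.

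**The concern.** The SAP's analysis section does not deliver all of the endpoint that its own objectives table defines, and it says that nothing has changed. A reader of the final report could not tell whether ventricular volume was left out of this comparison by decision or by oversight.

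The second matter is how the table can be interpreted. Total lesion counts and volumes at Study Visit 2 include whatever was present before the first dose. Responders and non-responders are separated by what happened to them afterwards, so nothing balances them at the start. The study itself asks whether patients with high disease activity are more likely to be responders, and that status can depend on pre-study T2 and gadolinium-enhancing lesions. A difference at Study Visit 2 could therefore have been present before treatment, and the planned tables give no means of seeing this.

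**Working it through.** **Measures in the definition against measures in the analysis**

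| Measure | Endpoint footnote c (synopsis; SAP section 5) | SAP 14.2.3 |
|---|---|---|
| T2 lesion volume | yes | yes |
| T2 lesion number | yes | yes |
| T1 lesion number | yes | yes |
| T1 lesion volume | yes | yes |
| Brain volume | yes (or surrogate) | yes, in cm³ |
| Ventricular volume | yes | **no** |

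The count is six against five, and SAP section 7 records no change.

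**Is a pre-treatment MRI value shown by responder status anywhere?**

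- SAP 17.1 lists twelve tables for this endpoint, 15.2.4.1.1 to 15.2.4.4.3 (four cohorts by the primary definition, B and C). All are titled at Study Visit 2. The pharmacogenetic counterpart, 15.2.11.4.1, is too.
- The only MRI change output is Table 15.2.8.1 (Cohort A, MRI sub-study set), with no responder version. SAP 8.2.2 allows subgroup analysis of tertiary endpoints as section 14 defines them, but 14.3.4 defines none.
- SAP 14.2.2 compares clinical characteristics by responder status. It includes EDSS, prior relapses and high-disease-activity status, but no MRI value.

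Responder-split outputs that show a parent-study MRI value: none.

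**Illustration of size**

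The documents give no precision, SD, responder share or correlation for this endpoint, so there is no stated figure to reproduce. From the documents: about 150 patients in the MRI sub-study (Protocol 4.1). Assumed: all 150 classifiable and split 75/75, baseline difference d0 = 0.3 SD, correlation r = 0.5 to 0.9 between baseline and Study Visit 2, equal SDs, and no group difference in course given baseline.

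- Expected unadjusted difference at Study Visit 2 = d0 × r = 0.3 × 0.5 to 0.3 × 0.9 = 0.15 to 0.27 SD.
- Unadjusted 95% half-width = 1.96 × √(1/75 + 1/75) = 1.96 × 0.163 = 0.32 SD.
- Adjusted 95% half-width = 0.320 × √(1 − r²): r = 0.5 gives 0.277; 0.7 gives 0.229; 0.8 gives 0.192; 0.9 gives 0.140.
- Chance that an unadjusted 95% CI excludes zero, Φ(d0·r/SE − 1.96) + Φ(−d0·r/SE − 1.96) with SE = 0.163: 15% at r = 0.5 and 38% at r = 0.9.

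Sensitivity to the assumptions: with d0 from 0.2 to 0.5 SD and a responder share of 50% or 30%, the carry-over is 0.10 to 0.45 SD and the chance of excluding zero is 9% to 79%. With 45 versus 105 patients the unadjusted half-width is 1.96 × √(1/45 + 1/105) = 1.96 × 0.178 = 0.35 SD. These formulas concern means on a scale where an SD is sensible. For lesion counts they are only a guide.

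**The reference scan for change**

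The brain-imaging objective in the protocol and SAP section 5 takes baseline as the last MRI before the first dose. SAP 14.3.4 and Protocol 9.4 take change from the last clinical visit in the parent studies, which SAP 14.3.4 labels Screening. Table 15.2.8.1 is titled as change from Baseline. Read literally, the 14.3.4 reference comes after parent-study dosing, so that change would not remove a pre-treatment difference.

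**The case against.** The strongest reply is that SAP 14.2.3 implements the protocol: the endpoint is defined at Study Visit 2, Protocol 9.4 plans it descriptively, and change is a separate tertiary objective. That stands. A reader might infer that the SAP weakened the endpoint by ignoring baseline. The documents do not support this; the limitation lies in the protocol's definition, and added baseline rows would be an improvement.

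Other tempting readings also go too far:

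- Omitting ventricular volume does not cause any baseline or head-size confounding. A raw ventricular volume would share the same limitation. It is also not lost from the study, because ventricular change remains in 14.3.4.
- That cm³ brain volume is confounded by head size cannot be asserted. No normalisation is stated, but the scan procedures are in a separate MRI manual that is not available here.
- A formal false finding is not at issue. The study is exploratory with no planned inference. The risk is misreading a difference, which matters because SAP section 4 intends these analyses for manuscripts.

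Three practical objections also stand in part. Comparable T2 data may exist only for ORACLE MS. Under the primary definition and Definition C a new T1 or T2 lesion makes a patient a non-responder, so lesion differences are partly built in and baseline adjustment does not remove that. Fewer than 150 patients may be classifiable, since SAP 8.2.2 expects missing MRI and retrospective EDSS data and codes incomplete all-negative cases as not determined. Sex and high-disease-activity status are compared by responder status in 14.2.2, but on the full analysis set, and the latter is only an indirect marker of MRI status.

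**Conclusion.** The ventricular-volume omission is wrong as written. It rests on the text alone and needs no assumption: six measures defined, five analysed, no change declared.

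The absence of any pre-treatment MRI value by responder status is a limitation of the protocol's own endpoint that can be eased at low cost. Its size cannot be established from the documents. The carry-over of 0.15 to 0.27 SD and the narrowing from 0.32 to between 0.28 and 0.14 SD depend on the assumed split, imbalance and correlation. They show that a pre-treatment difference could matter, not that one exists.

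**What to change.** 1. Add ventricular volume at Study Visit 2 to SAP 14.2.3 and Tables 15.2.4.x, or declare and justify its removal in SAP section 7.
2. In Tables 15.2.4.x, beside each Study Visit 2 value, show by responder status the value from the last MRI before the first dose where comparable data exist. Add, as a supportive descriptive row, the baseline-adjusted difference with 95% CI (log scale for volumes, a count model for lesion numbers).
3. Reconcile the reference scan between the endpoint definition and SAP 14.3.4 and Protocol 9.4. Only then show percentage brain volume change by responder status.
4. State in the SAP whether brain volume in cm³ is normalised for head size.
5. Note beside the lesion results that new lesions help to define non-response under the primary definition and Definition C, and read them together with Definition B, which uses only subsequent treatment.

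The cost is SAP wording, extra rows in twelve listed tables and a simple model. No new patient assessment is needed, but someone must establish which parent-study MRI values are comparable with the sub-study readings. Patients without a usable baseline scan drop out of the added rows only, and the T2 rows may be limited to ORACLE MS.
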